Concealed penis in pediatric age group; A comparison between three surgical techniques.

Dear editor-in-chief of the BMC Urology;

I have the honor to submit our original research article entitled "Concealed penis in pediatric age group; A comparison between three surgical techniques" by [name] aiming at your helpful review and hopefully your acceptance for publication in your respectable journal "BMC Urology".

We believe that this manuscript is appropriate for publication in **"BMC Urology"** because it compares three surgical techniques in the management of congenital concealed penis in the pediatric age group which is included in the aims and scope of your respectable journal.

This manuscript has not been published and is not under consideration for publication elsewhere. We have no conflicts of interest to disclose and our manuscript had not received any financial funds. All of the co-authors, as well as the Alexandria University Scientific Committee, approved its publication and informed consent was signed by the parents explaining the study.

Thank you for your consideration! Waiting for your respectable reply.

Sincerely,

[name]*

Corresponding Author

Associate Professor of Pediatric Surgery,

Faculty of Medicine, Alexandria University, Egypt

Address: Faculty of Medicine, Alexandria University, Egypt

[contact]

ORCID ID: [name]

Email: [contact] [contact]

NCT number: 0305434

Document date: September 2022

Abstract

Background: Comparison between three different surgical techniques in the management of concealed penis. **Methods:** This prospective interventional non-randomized study included 150 pediatric patients with concealed penis. They were distributed equally into three groups; group A; patients treated by anchoring the penile skin dermis to Buck's fascia at the penile base at 3 & 9 o'clock points using PDS 5/0 (phallopexy), group B; patients treated by complete dissection and excision of dartos fascia & group C; patients treated by phallopexy as in group A after complete dissection and excision of dartos fascia. Follow-up at the end of the 1st post-operative week and then monthly for 6 months as regards penile skin congestion and/or necrosis, wound infection, edema, and/or re-retraction was carried out. Also, a questionnaire of parents about the follow up points was done

Keywords: Concealed, phallopexy, dartos excision, degloving, penile reretraction.

Background

The concealed penis is a congenital anomaly in which a normal size penis is hidden in the pre-pubic fat with the glans penis that does not project from the pubic or scrotal skin. (Figure 1) This condition is usually associated with poor cosmoses, difficult accessibility resulting in poor hygiene, social embarrassment, recurrent balanitis, difficult urination, and secondary phimosis. (1,2)

The pathogenesis of this anomaly was attributed to an excessive development of the penile dartos fascia retracting the penis inwards, an insufficient attachment of the penile skin to the deep penile tissues at the penile base, and/or tight phimosis which is often present. Also, excessive prepublic fat is usually present and worsens the appearance of the abnormality but does not explain the pathology by itself. (3)

Another variety of buried penis is the congenital mega-prepuce in which a redundant inner preputial skin covers the glans penis in an average size penis in association with severe phimosis. These patients usually complain of voiding difficulties as the urine traps in the redundant dome-like mega-prepuce. This variety requires different treatment modalities (4)

The difference in the outcome of different corrective for such conditions was not compared widely in the literature so this study aimed to compare three different surgical techniques. The aim of this study was the comparison three different surgical techniques used in the management of concealed penis in the pediatric age group. The 1st technique is in the form of anchoring the penile skin dermis to Buck's fascia (phallopexy) at the penile base, the 2nd one is in the form of complete dissection and excision of dartos fascia and the 3rd technique is in the form of phallopexy after complete dissection and excision of dartos fascia

Methods

This study is a prospective interventional non-randomized study. It included 150 uncircumcised patients in the pediatric age group who presented to Elshatby University Hospital with a concealed penis between June 2018 and June 2021. The main complaint of the parents of the studied patients was appearing small size penis, unapparent penis, difficult cleaning, and/or unsatisfaction.

The inclusion criteria included patients with a buried penis at or below the pubic skin level with a stretched penile length for all of them within the normal range according to their ages as titrated in the literature. (5)

Patients with any associated anomalies like hypospadias, torsion, penoscrotal web, micropenis, mega-prepuce, or chordae were excluded from the study.

The included patients were distributed non-randomly into three groups. The procedure was chosen according to the operative findings as dartos dissection and excision were recommended in patients with a thick abnormal dartos alone, phallopexy was recommended in case of absence of normal penile fixation alone and a combination of both techniques was recommended when the two pathologies were found. Group A included patients who were treated by anchoring the penile skin dermis to Buck's fascia (phallopexy) at the penile base without excision of dartos fascia, group B included patients who were treated by complete dissection and excision of dartos fascia only and group C included patients who were treated by phallopexy as in patients of group A but after complete dissection and excision of dartos fascia. The choice of the procedure was random among the studied patients

All of the studied patients had routine pre-operative laboratory investigations including CBC, CT, BT, PT, PTT, and INR. Informed consent was signed by the parents or caregivers after a complete explanation of the study design, its publication as well as any possible complications.

All of the studied patients were operated on under general anesthesia with skin preparation using povidone-iodine. The prepuce was also retracted backward and cleaned completely from any smegma with povidone-iodine.

The procedure was started by the application of two forceps mosquitos at the preputial mucocutaneous junction with formal circumcision leaving about 5 mm of the mucosal collar from the sub-coronal level. (Figure 2; A & B). This is followed by the application of two curved mosquito forceps at the sub-coronal level at three and nine o'clock points retracting the penis outwards during the whole procedure taking care of non-rotating the penis along with the operation by keeping retraction in the mid-line continuously. (Figure 2; C).

Complete penile degloving in the sub-dartos plane was then started with meticulous dissection of the skin and dartos fascia out of Buck's fascia down to the level of penoscrotal junction ventrally and penopubic angle dorsally taking care of both neurovascular bundle and skin vascularity. On the dorsal aspect; the fundiform ligament - which is usually attached to the distal or midpenile shaft - was identified and dissected to increase the penile length. The dissection was completed circumferentially releasing all of the abnormal bands anchoring dartos fascia to Buck's fascia. (Figure 2; D)

To avoid penile re-retraction; one of the following techniques was done. (Figure 2; B). In patients of the group, A phallopexy was done in the form of anchoring the penile Buck's fascia to the penile skin dermis at the penile base at three & nine o'clock points without excision of dartos fascia. This was done using PDS 5/0 taking care of non-rotating the penis while taking the stitches by keeping retraction just in the midline. Patients of group B were managed by complete circumferential dissection and excision of dartos fascia only. This was done in a meticulous fashion taking care of skin vascularity. Lastly, patients of group C were managed by phallopexy as in patients of group A but after complete dissection and excision of dartos fascia. (Figure 2; E&F)

After removal of the retracting forceps; the skin was repositioned over the degloved penis and was sutured distally to the mucosal collar in a subcuticular fashion using Vicryl 6/0. (Figure 2; G, H & I). A compression dressing was applied over the wound after the application of local antibiotic cream.

Removal of the dressing was done on the 1st postoperative day with repeated application of local antibiotic cream three times daily for one week in addition to oral anti-inflammatory (NSAIDs) and anti-edematous for five days.

Follow-up of the appearance of the penile skin (congestion, necrosis), wound infection, edema, and or re-retraction at the end of the 1st postoperative week and then monthly for six months was done. Comparing the follow-up results between the three studied groups was carried out using the appropriate statistical method

Also, a questionnaire of parents about the follow up points was done

Statistical Analysis

Data were coded, reviewed, and analyzed using the SPSS version 25.0 (Armonk, NY: IBM Corp). The Kolmogorov-Smirnov (KS) test was used to test the normal distribution of the data. Quantitative data were expressed as median and range. Qualitative data were expressed as frequency and percentage. Kruskal-Wallis test was used to detect any statistically significant differences between three or more independent non-normally distributed groups. A pairwise comparison was conducted among significant groups. The Chi-square test was used to test the association between two categorical variables or to detect the difference between two or more proportions and whenever χ^2 was not valid, Monte Carlo exact probability was used for RxC tables. The statistical analysis was carried out in the Community Department, Faculty of Medicine, Alexandria University

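### The Methods say the procedure was chosen by operative findings and also that it was random; under the findings rule, technique cannot be separated from pathology

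*Protocol*

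**What the plan says.** The abstract states "This prospective interventional non-randomized study included 150 pediatric patients with concealed penis" and adds "They were distributed equally into three groups". The Methods open with "This study is a prospective interventional non-randomized study".

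The allocation paragraph of the Methods then makes three statements in this order:

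- "The included patients were distributed non-randomly into three groups".
- "The procedure was chosen according to the operative findings". The rule is three-way: thick abnormal dartos alone leads to dartos excision (group B), absent fixation alone leads to phallopexy (group A), and "a combination of both techniques was recommended when the two pathologies were found" (group C).
- "The choice of the procedure was random among the studied patients".

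The Background gives the purpose: "this study aimed to compare three different surgical techniques". The Statistical Analysis section names Kruskal-Wallis, chi-square and a Monte Carlo exact test for comparing groups.

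**The concern.** A procedure chosen by what the surgeon finds at operation is not a procedure chosen at random. The two statements describe different studies, and nothing in the document withdraws either.

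The choice between them decides what the results can mean. Under random choice, a difference in re-retraction, oedema or necrosis could be credited to the technique. Under the findings rule, the three groups differ in their anatomy as well as in their operation, and the sentence on random choice invites exactly the conclusion that the rule rules out.

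**Working it through.** **1. The allocation statements side by side**

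| Place in protocol | Allocation |
|---|---|
| Abstract | Non-randomized; three equal groups |
| Methods, opening | Non-randomized |
| Methods, allocation paragraph, start | Non-random |
| Same paragraph, middle | By operative findings, one procedure per finding |
| Same paragraph, last sentence | Random |

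Four statements agree and one does not. No sequence, list, block or other chance device is described. The weight of the text therefore favours allocation by findings, but the text does not settle it.

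**2. What the findings rule implies**

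Absent fixation alone goes to A, thick dartos alone to B, and both to C. If the rule was followed, each pathology appears in one group only. No patient with a given pathology received another technique, so the data contain no comparison of techniques within a pathology. The tests named are unadjusted, but with no overlap an adjusted analysis would have nothing to work with either.

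**3. How large the confounding could be (illustration)**

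The protocol gives no event risks, so those below are assumptions. Group size is 150 / 3 = 50, taking the abstract's equal distribution to mean 50 each. There is no technique effect: risk depends on pathology alone. The test is Pearson chi-square on the 3 × 2 table with 2 degrees of freedom at a nominal 5% level.

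- Rejection probability = the sum, over all 51³ = 132,651 possible outcomes, of Bin(a; 50, pA) × Bin(b; 50, pB) × Bin(c; 50, pC), wherever the test rejects.
- The exact fallback in the Statistical Analysis section is taken to apply when an expected count is below 5. That threshold is an assumption.
- For comparison, randomly allocating the same case mix gives every group the common risk (pA + pB + pC) / 3, for example (5 + 5 + 10) / 3 = 6.7%.

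| Risk in A / B / C | Findings rule: chi-square | With exact fallback | Common risk if random | Random: chi-square | With exact fallback |
|---|---|---|---|---|---|
| 5 / 5 / 7.5% | 7.0% | 5.9% | 5.8% | 4.4% | 3.5% |
| 5 / 5 / 10% | 15.3% | 13.6% | 6.7% | 4.6% | 3.8% |
| 5 / 5 / 15% | 42.7% | 40.7% | 8.3% | 4.8% | 4.2% |
| 5 / 5 / 20% | 70.9% | 69.7% | 10.0% | 4.8% | 4.5% |

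Starting from a higher base risk, 10 / 10 / 15% gives 11.2% (11.0% with the fallback) and 10 / 10 / 20% gives 30.0% (29.9%). These figures measure confounding under the findings rule. They do not measure the effect of the contradictory wording.

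**4. The equal groups**

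If group membership is left to chance with shares p1, p2, p3, then P(50, 50, 50) = 150! / (50!)³ × (p1 p2 p3)^50.

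- Shares of 1/3 each, which is the maximum: 0.0055, or about 0.5%.
- Shares of 30 / 30 / 40%: 0.0013.
- Shares of 25 / 25 / 50%: about 1 in a million.

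This applies equally to unrestricted findings-based allocation and to simple randomisation. An exact three-way split suggests a further step, such as a quota or blocking, that the document does not state.

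**The case against.** The strongest reply is that the sentence on random choice is a slip. The design is labelled non-randomized twice and the allocation non-random once before the reader reaches it, and confounding by indication is a known limitation of an openly non-randomized study. That reading is plausible. It does not remove the sentence, which misstates the fact that governs interpretation, and no label in the document tells the reader that the technique comparison is limited.

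Second, the rule is worded as a recommendation, and the groups are defined by the treatment received. Departures could leave some overlap between pathology and technique. This stands as a condition: the absence of overlap holds only if the rule was followed. No departures are described.

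Third, a quota per group or blocked randomisation would give equal groups by design. That also stands. The equal split is therefore not a second contradiction, only a sign that part of the mechanism is unstated.

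Fourth, the rejection rates rest wholly on assumed risks, and at the mildest setting with the exact fallback the result (5.9%) is close to nominal. This is correct. The range shows that the bias may be small or large, and the document gives no basis for choosing within it.

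An unseen SAP does not answer the main point, because the conflict lies between sentences of the protocol itself.

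**Conclusion.** The concern holds. The protocol gives two incompatible accounts of how all 150 patients came to their procedure, and every between-group comparison depends on which is true. This must be corrected.

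If the findings rule was used and followed, group differences describe technique and pathology jointly, and no analysis of these data can divide them. On the assumed risks above, pathology alone would produce a significant result between about 6% and 71% of the time at a nominal 5% level, against about 4% to 5% under random allocation of the same patients. If the choice was truly random, this confounding does not arise, but the non-randomized label and the findings rule are then wrong.

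**What to change.** Reconcile the abstract, the opening of the Methods and the allocation paragraph to the one mechanism actually used, and say how the equal group sizes arose.

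- If operative findings decided: delete the sentence on random choice. State that group differences reflect technique and pathology together and cannot be attributed to technique. Report any departures from the rule.
- If the choice was random: describe the chance mechanism, and correct the non-randomized label and the findings rule.

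The cost is a change of wording and, in the first case, a narrower conclusion. No new data are needed. Nothing here bears on which procedure suits which finding.

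### Does the analysis of the follow-up signs stop at a three-group p-value that cannot show which technique differs from which?

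*Protocol*

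**What the plan says.** The Background gives the purpose: "The aim of this study was the comparison three different surgical techniques used in the management of concealed penis". The follow-up paragraph of Methods lists what is observed: "Follow-up of the appearance of the penile skin (congestion, necrosis), wound infection, edema, and or re-retraction". It then adds: "Comparing the follow-up results between the three studied groups was carried out using the appropriate statistical method".

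The Statistical Analysis section takes up the methods in this order:

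1. Categorical summaries: "Qualitative data were expressed as frequency and percentage".
2. Quantitative comparison: "Kruskal-Wallis test was used to detect any statistically significant differences between three or more independent non-normally distributed groups".
3. The pairwise step: "A pairwise comparison was conducted among significant groups".
4. Categorical comparison: "The Chi-square test was used to test the association between two categorical variables or to detect the difference between two or more proportions".
5. The fallback when chi-square "was not valid, Monte Carlo exact probability was used for RxC tables".

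No risk difference, ratio or confidence interval is named. The pairwise sentence names neither a test nor a data type.

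**The concern.** The pairwise sentence stands directly after Kruskal-Wallis and before chi-square, and no pairwise sentence follows the categorical tests. Congestion, necrosis, infection, edema and re-retraction are given no measurement scale and most naturally read as present/absent or graded, so the categorical tests are the ones that matter here. If the pairwise step belonged to Kruskal-Wallis alone, each sign would end in one global p-value.

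Comparing three techniques means three contrasts: A-B, A-C and B-C. A global p-value says that the groups are not all alike, but not where or by how much they differ. A non-significant one could also be misread as no difference, although 50 per group leaves sizeable differences open. On that reading the analysis would fall short of the aim.

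**Working it through.** **Inputs.** The Abstract gives 150 patients in three equal groups, so 150/3 = 50 per group. The protocol states no event rate, significance level or sample-size calculation, so there is no planned figure to reproduce. All counts below are assumed, as are a two-sided 0.05 level and the usual rule that chi-square is valid when every expected count is at least 5.

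**Step 1: can a global p-value hide the pattern?** For three groups of 50 with counts x, mean count m and overall proportion p, chi-square = Σ(x − m)² / [50·p·(1 − p)] on 2 df, and its p-value is exp(−chi-square/2).

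- 8/8/1: m = 17/3 = 5.667 and p = 17/150 = 0.1133. The sum of squares is 5.444 + 5.444 + 21.778 = 32.667 and the denominator is 50 × 0.1133 × 0.8867 = 5.024. Chi-square = 6.50, p = 0.039.
- 8/1/8 has the same counts in another order, so chi-square is again 6.50 and p = 0.039.
- 10/5/2 has the same mean, and 18.778 + 0.444 + 13.444 is again 32.667, so once more p = 0.039.

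Three patterns, one p-value: the statistical premise of the concern is correct.

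**Step 2: does the plan stop there?** Set the sentences side by side.

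- The pairwise sentence refers to groups found significant. It does not mention Kruskal-Wallis, medians or quantitative data; any limit is inferred from its position in one short paragraph.
- The chi-square sentence covers two proportions as well as more than two, so a two-group comparison is within the stated method.
- Methods leaves the comparison of follow-up results to a suitable method and excludes no pairwise test.

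Nothing in these sentences confines the categorical signs to a global test.

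**Step 3: what the pairwise step gives.** For 8 v 1 of 50, chi-square = 100 × (8×49 − 1×42)² / (50×50×9×91) = 12,250,000/2,047,500 = 5.98, p = 0.014. The smallest expected count is 4.5, so the exact test would apply: Fisher p = 0.031. For 8 v 8, p = 1.0. In 8/8/1 this singles out C, and in 8/1/8 it singles out B. In 10/5/2, only 10 v 2 is separated (p = 0.014; 10 v 5 gives p = 0.161 and 5 v 2 exact p = 0.436). The three patterns are told apart.

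The gate is also sound for three groups. If all three are alike, a false pairwise claim first needs a false global one. If exactly two are alike, only one pairwise null is true. So, for a single outcome, error stays near 0.05, not at the 1 − 0.95³ = 14.3% of three ungated independent tests.

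**Step 4: are size and precision lost?** Frequencies and percentages with 50 per group are all that a risk difference and its interval need. For 8 v 1 of 50, the Wilson 95% limits are 8.34% to 28.51% around 16%, and 0.35% to 10.50% around 2%. Newcombe's interval for the 14.0-point difference is then:

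- lower: 14.0 − √[(16 − 8.34)² + (10.50 − 2)²] = 14.0 − 11.4 = 2.6
- upper: 14.0 + √[(28.51 − 16)² + (2 − 0.35)²] = 14.0 + 12.6 = 26.6

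A reader can get this from the reported table alone.

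**Step 5: does the gate hide a real contrast?** Take 8/5/2: chi-square = 18/(50 × 0.1 × 0.9) = 4.00, p = exp(−2) = 0.135, so no pairwise test follows. The first-minus-third difference is 12.0 points with 95% CI −0.2 to +24.8. The pairwise chi-square p is 0.046, but Fisher's is 0.092 and the interval includes zero. This shows imprecision, not an established difference that the gate suppressed.

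**The case for a change.** The strongest reply is that, even if the pairwise sentence is general, it yields p-values only after a significant global test and names no effect size or interval. Equal counts in two groups leave about ±7 points open at 0 of 50, ±10 at 2 of 50 and ±16 at 10 of 50, so a non-significant sign is no evidence of equivalence. The protocol has its own statistics section, so the ambiguity is in its text, and three differences with intervals per sign would cost little.

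Some of this stands. Intervals would inform more than p-values, and the sentence order is ambiguous. But neither point makes a stated rule wrong, and the protocol nowhere says that a non-significant result will be taken as equivalence. Naming the pairwise test, its scope and the estimates is detail that a protocol commonly leaves to the statistical analysis plan.

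Some examples that could be used to press the point are fragile. In 10/3/3 and 12/4/4 the first group seems to differ from both others by chi-square (p = 0.037 and 0.029), but Fisher's test gives 0.071 and 0.054. The 8/8/1 and 8/1/8 pair makes the logical point without that weakness, and there the pairwise step resolves it.

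Intervals would also leave a separate difficulty untouched: Methods says both that operative findings decided the procedure and that the choice was random. If findings decided it, every contrast mixes technique with pathology, whatever its interval.

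**Conclusion.** The concern does not hold. A global p-value alone indeed cannot locate a difference, but the protocol does not say that the analysis ends there. Its pairwise step is worded without restriction, chi-square is stated for two groups as well as more, and frequencies and percentages by group let all three contrasts be rebuilt. Followed as written, with pairwise comparison after a significant global test, the method serves the stated aim.

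No stated figure or rule is wrong, so there is no numerical effect to report; every count used above is assumed. The conclusion rests on reading the pairwise sentence as its words allow, on equal groups of 50, and on a statistical analysis plan being the usual place for the missing detail. If the pairwise step were in fact confined to Kruskal-Wallis, the tests for the categorical signs would be less informative, but the reported counts would still let a reader form each contrast.

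### Only unadjusted tests are named for categorical outcomes of groups called non-random: reconcile the allocation statements first, then show one age-adjusted comparison beside the chi-square, with neither read as the effect of technique

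*Protocol*

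**What the plan says.** The Methods section opens its design description with "This study is a prospective interventional non-randomized study". The allocation paragraph repeats this ("The included patients were distributed non-randomly into three groups") and gives a rule: "The procedure was chosen according to the operative findings". Thick dartos alone leads to excision, absent fixation alone to phallopexy, and both together to the combined operation. The same paragraph ends with "The choice of the procedure was random among the studied patients".

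Eligibility required children "with a stretched penile length for all of them within the normal range according to their ages", so each child's age had to be known.

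On outcomes, the Methods give the surgical purpose ("To avoid penile re-retraction; one of the following techniques was done") and say of the analysis: "Comparing the follow-up results between the three studied groups was carried out using the appropriate statistical method". The Statistical Analysis section then names the tests. For quantitative data it names Kruskal-Wallis with pairwise follow-up. For categorical data it says "The Chi-square test was used to test the association between two categorical variables" or to compare proportions, with Monte Carlo exact probability where chi-square is not valid. It names no regression, stratification, matching or propensity method, and it does not say which variable each test was applied to.

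**The concern.** A chi-square test on a group-by-outcome table attributes the whole difference to group. That is defensible when groups differ only by chance. It is weaker when the protocol itself calls the groups non-random and a baseline variable is available but not used in the categorical comparisons. If age differs between groups and also predicts re-retraction, part of an unadjusted difference is an age effect.

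The allocation statements decide how much this matters. If the choice was random, only chance imbalance is at stake. If it followed the operative findings, there is a larger problem that age cannot address: the three groups are three pathologies, each given its own technique.

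**Working it through.** **Inputs from the protocol.** 150 patients distributed equally: 150 / 3 = 50 per group. The protocol gives no event rate, significance level, effect size or age distribution, so there is no figure of its own to reproduce.

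**Assumed inputs.** Nominal 5% level; no true technique effect; risk of re-retraction 12% (range 6% to 20%) at mean age in the unshifted groups; age standardised and shifted by 0 to 0.8 SD in one group; odds ratio (OR) of 1.3 to 2.5 per SD of age; where stated, an operative-finding OR of 2 or 3 in that same group.

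**Step 1. Can the operative finding be adjusted for?** Let D = thick dartos and F = absent fixation. Under the stated rule, group A has D = 0, F = 1; group B has D = 1, F = 0; group C has D = 1, F = 1. With group indicators, D = B + C and F = 1 − B. Intercept, two group terms, D and F make five columns of rank 3. Once group is in the model the findings add nothing, so the effect of technique cannot be separated from them.

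**Step 2. Size of an age distortion.** On the odds scale the distortion of the shifted group is roughly OR^shift:

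- 0.5 SD, OR 1.5: 1.5^0.5 = 1.22
- 0.5 SD, OR 2: 2^0.5 = 1.41
- 0.8 SD, OR 2: 2^0.8 = 1.74

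**Step 3. Age alone.** False positives by simulation (3 x 50 patients, 4,000 replicates, Monte Carlo standard error about 0.3 points at 5%), Pearson chi-square against the 2-df penalised likelihood-ratio test from a Firth logistic model with group and age, 12% risk:

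| Shift (SD) / OR per SD | Chi-square | Age-adjusted |
|---|---|---|
| 0 / 1.5 | 4.5% | 4.2% |
| 0.3 / 1.5 | 5.7% | 4.9% |
| 0.5 / 1.5 | 6.0% | 4.4% |
| 0.5 / 2 | 8.6% | 4.9% |
| 0.8 / 1.5 | 8.8% | 4.5% |
| 0.8 / 2 | 16.4% | 4.8% |
| 0.8 / 2.5 | 25.9% | 4.3% |

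The gain depends on risk as well: 0.8 / 1.5 gives 6.2% vs 3.2% at 6% risk and 10.0% vs 4.5% at 20%.

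**Step 4. Operative finding added.** Same set-up, 12% risk, operative-finding OR 2:

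| Age effect | Chi-square | Age-adjusted |
|---|---|---|
| No shift | 24.1% | 23.6% |
| Same direction, 0.5 / 1.5 | 40.5% | 23.0% |
| Same direction, 0.8 / 2 | 70.5% | 25.2% |
| Opposite direction, 0.3 / 1.5 | 18.2% | 23.0% |
| Opposite direction, 0.5 / 1.5 | 13.9% | 21.6% |
| Opposite direction, 0.5 / 2 | 9.6% | 22.2% |
| Opposite direction, 0.8 / 2 | 5.7% | 17.4% |

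Repeat runs of the last two rows gave 8.8% vs 20.4% and 3.8% vs 17.2%. At 6% and 20% risk, the opposite-direction 0.5 / 2 case gives 6.7% vs 12.9% and 10.8% vs 29.2%. With operative-finding OR 3 at 12% risk it gives 28.2% vs 50.1%; with OR 3 and no shift, 57.8% vs 59.0%.

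Step 2 explains the opposite-direction rows. For 0.5 / 2 the unadjusted odds ratio is about 2 / 1.41 = 1.4, because two biases partly cancel. Adjustment removes the age part and leaves the operative-finding OR of 2 exposed.

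**Step 5. Price.** The model has three slope terms. Without an operative-finding effect, mean events were 9.6 to 15.6 at 6% risk (9.6 / 3 = 3.2 to 15.6 / 3 = 5.2 per term) and 18.9 to 27.9 at 12% (6.3 to 9.3 per term). The standard error of the shifted group's log odds ratio changes by +1% to +12% at 12% risk, and by −1% to +13% over 6% to 20%.

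**The case against.** The strongest objection is that covariate adjustment is commonly left to a statistical analysis plan, and none is shown. That stands against calling this a proven omission. It does not remove the point, because the Statistical Analysis section is a specific account, in the past tense, of the tests used. Unadjusted tests for groups called non-random are therefore a stated choice. If an unseen plan already adds an adjusted analysis, that part of the request is met.

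Second, neither reading of the allocation paragraph guarantees a gain. Under random choice the chi-square test holds its size, apart from chance imbalance. Under allocation by findings the main bias is untouched, and adjustment can make the comparison look worse. This stands. It is why the adjusted result belongs beside the chi-square and not in its place.

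Third, the choice of one outcome, one time point and one covariate is the reviewer's. The protocol names no primary outcome, and its statement about re-retraction describes surgical purpose. That is fair, and it is a reason to fix the model in advance of fitting and label it as added.

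A reader might infer that age was never compared between groups. The protocol does not establish this: the Kruskal-Wallis test is tied to no variable, the listed follow-up outcomes are qualitative, and age is a plausible target. Such a test would still be a baseline comparison and not an adjustment.

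**Conclusion.** The point holds as a minor, conditional suggestion with medium confidence. Only unadjusted tests are named for categorical outcomes, and the allocation statements contradict each other. That contradiction matters more than the missing covariate, because it decides whether any between-group test can speak to technique.

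The actual size of the age problem is unknown; every rate and odds ratio above is assumed. Under those assumptions age adjustment changes little for mild imbalance and brings false positives back to about 5% for strong imbalance. It does nothing against operative finding alone. With age opposing an operative-finding OR of 2 (0.5 SD, OR 2 per SD, 12% risk), it takes false positives from about 9% to about 20%.

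Two stronger readings are tempting. One is that age confounding has distorted the results; the protocol shows neither an age difference by group nor a link between age and outcome. The other is that adjusting for age would make the three techniques comparable; under the stated allocation rule, technique and finding are the same variable, so it would not.

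**What to change.** 1. Reconcile the three allocation statements: non-random, by operative findings, and random.
2. If operative findings decided the procedure, state that technique coincides with pathology, that no between-group test, adjusted or not, isolates the effect of technique, and limit the conclusion to match.
3. Report age by group. If the Kruskal-Wallis test already covers this, say so.
4. Keep the chi-square test. Beside it, report one comparison of re-retraction by month 6 from a Firth-penalised logistic model with group and linear age as the only terms, giving adjusted odds ratios with 95% confidence intervals. Label it as added after the stated analysis.
5. Show both results whichever way they differ. Say that the adjustment addresses age imbalance only, leaves confounding by operative finding in place, and may move the difference in either direction.

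The cost is a small extra analysis on a variable that eligibility already required. The main drawback is imprecision if events are few: at 6% risk even this small model would rest on about 10 to 16 events.
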